## 5.2 Recruitment Methods

To conduct this pilot RCT, we will recruit from two populations of participants; primary care physicians, and 100 patients of those physicians who have been newly prescribed a certain antidepressant.

### 5.2.1 Physician Participants

Physician participants will be recruited through presentations of the study at UM DFM Grand Rounds and faculty business meetings, clinical site staff meetings, and targeted emails and letters to all UM DFM physicians who treat patients.

Study staff may also call providers who have not responded to recruitment letters/emails up to two times. In the event that a potential participant is eligible to participate in the study, except for the fact that their primary care provider is not yet participating, we will attempt to recruit the provider through up to two additional emails and two additional phone calls. Any provider who indicates that they are not interested in participating will not be contacted further. Provider participants will receive no incentives for their participation in this study.

### **5.2.2 Patient Participants**

For patient participant recruitment, once UM DFM physicians have been consented and enrolled, we will recruit their patients who have new prescription for an antidepressant (within the past 4 weeks prior to screening) from the following list: citalopram (Celexa), escitalopram (Lexapro), fluoxetine (Prozac, Prozac Weekly, Rapiflux, Sarafem, Selfemra), fluvoxamine (Luvox, Luvox CR), paroxetine (Paxil, Paxil CR), sertraline (Zoloft), duloxetine (Cymbalta, Irenka), venlafaxine (Effexor, Effexor XR), nortriptyline (Aventyl, Pamelor), bupropion (Forfivo, XL, Wellbutrin, Wellbutrin SR, Wellbutrin XL), mirtazapine (Remeron, Remeron Soltab), or vortioxetine (Trintellix). These potential patient participants will be identified through direct provider referral via flags to providers in MiChart and patient brochures, signs and brochures posted in the UM DFM clinical sites, and targeted recruitment letters, followed by recruitment phone calls, to patients who meet eligibility criteria as identified in MiChart.

To facilitate the delivery of targeted recruitment letters to potential patient participants, we will obtain lists of potentially eligible participants from the Data Office on a rolling basis. Letters will be batched and sent in waves.

To thank patient participants for their participation in this study, we will provide a \$20 check after each data collection assessment (up to \$60 for intervention group participants, and up to \$80 for waitlisted control group participants). All incentives will be pro-rated for partial study completion. Incentives will be distributed by the UM Treasurer's office through the Human Subjects Incentive Program.

### **5.3 Informed Consent Procedures**

We will obtain written informed consent from both groups of participants in this study (physicians and their patients). First, research staff (including project coordinators and research assistants) will describe the study to physician participants and obtain written informed consent. Once physician participants are consented and enrolled, we will then recruit patients of those physicians who are newly prescribed a certain antidepressant. Research staff (including project coordinators and research assistants) will explain the study to patient participants and written informed consent will be obtained. Any participant who is unable to provide consent for himself/herself will be excluded from this study. Whenever possible, study staff will seek to conduct consent and baseline data collection at the MCRU site in order reduce burden on participants.

## 5.4 Inclusion/Exclusion Criteria

### **5.4.1 Physician Participants**

To be included in this pilot trial, physician participants must:

- Be a practicing physician at one of the six UM DFM clinical sites
- Be willing to utilize PGx test results to adjust antidepressant therapy for their participants enrolled in the study
- Be willing to allow study staff to contact their patients
- Self-report that they are willing to prescribe antidepressants
- Be at least 21 years old

Physician participants will be excluded from this pilot trial if they:

- Do not meet inclusion criteria

### **5.4.2 Patient Participants**

To be included in this pilot trial, participants must:

- Be a patient of a participating physician
- Have a new prescription for a certain antidepressant recorded in MiChart (within the previous 4 weeks prior to screening)
- Be currently taking the new antidepressant
- Be willing to undergo PGx testing via single tube blood draw
- Be at least 18 years old

Participants will be excluded from this pilot trial if they:

- Do not speak English
- Have previously undergone PGx testing
- Are unable to provide their own consent to participate in the study
- Have been taking the new targeted antidepressant for longer than 4 weeks (prior to screening)

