## 2.0 Introduction

According to the Centers for Disease Control and Prevention, between 2011 and 2014, 10.7% of Americans reported taking at least one antidepressant in the past month. [1] Antidepressants were the third most commonly used medication after cholesterol and pain medications.

Antidepressants are prescribed for the management of depression, anxiety, and other conditions. Given that the time from initiation of pharmacologic treatment to clinical effect takes two to four weeks,[2, 3] coupled with the fact that the initial medication may not be effective, thus necessitating adjustments to dosages or medications, treatment with an antidepressant can be a long and complicated process, during which patients still experience symptoms.

Strategies to improve treatment often include switching patients to a different antidepressant or prescribing an additional antidepressant.[4]

One reason for poor response to antidepressants can be attributed to the drug metabolism process. Many of the most commonly prescribed antidepressants undergo phase one xenobiotic metabolism by a class of enzymes in the P450 superfamily. This family of enzymes exhibits a high degree of genetic polymorphism, resulting in variable metabolism. Because of this variation in P450, we can classify individuals as poor, intermediate, extensive, and ultra-rapid metabolizers. The consequence of this population heterogeneity is that medications are metabolized at different rates and plasma concentrations of specific drugs can be outside of the optimal range, which may result in adverse drug events or lack of therapeutic effect. Because of these two medication outcomes, treatment may be discontinued.

Pharmacogenomic (PGx) testing of several cytochrome P450 genes and the most frequently described functional variants (CYP2D6, CYP2C9, CYP2C19, and CYP1A2) can be used to predict the metabolic capacity of an individual. For example, it is estimated that 5-10% of Caucasian individuals are poor metabolizers and 1-2% are ultra-rapid metabolizers based on CYP2D6 phenotypes.[5] By knowing a patient's genetic information and the drug's major metabolic pathway, we can prospectively assess the appropriateness of specific medications, modifying the dosing or using enhanced monitoring. By identifying the approximately 10% of individuals who will not metabolize antidepressants properly via the CYP2D6 pathway, we may be better able to identify effective treatment options and minimize adverse effects.

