## 3.0 Objectives

PGx testing could greatly improve the use of antidepressants by aiding prescribers in identifying proper medications for individual patients; thus potentially improving medication adherence, as well as reducing symptoms and antidepressant side effects.

This pilot study will explore the use of PGx testing in primary care, and is guided by several specific aims:

Specific Aim 1: To determine the effect of PGx testing on the primary outcome of physician treatment decisions, as measured by the change in the proportion of patients who are prescribed medications at baseline that are contraindicated according to the PGx test, compared to the proportion at six-month follow-up.

Specific Aim 2: To determine the effect of PGx testing on secondary outcomes measures of interest, including change in symptoms and severity and medication adherence from baseline to six-month follow-up.

Specific Aim 3: To determine the acceptability of PGx testing in primary care among patients and physicians.

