**Table 2. Patient Participant Measures**

Construct	Measure	Assessment Time			
		Baseline (via paper survey)	3 months (via phone)	6 months (via phone)	9 months (Control Only; via phone)
Reason antidepressant was prescribed		X	X	X	X
Depression Symptoms and Severity	Personal Health Questionnaire Depression Scale (PHQ-8)	X	X	X	X
Anxiety Symptoms and Severity	Generalized Anxiety Disorder 7-Item Scale (GAD-7)	X	X	X	X
Functional Health Status	12-Item Short Form Survey (SF-12)	X	X	X	X
PGx Knowledge	Investigator Developed	X			X
Missed days of work	Work Productivity and Activity Impairment Questionnaire (WPAI)	X	X	X	X
Demographic information		X			
Health history	Smoking history, BMI	X			
Healthcare utilization	Physician visits, hospital and ER admissions	X	X	X	X
Adverse Drug Reactions	Antidepressant Side- Effect Checklist (ASEC)	X	X	X	X
Medication and medication changes	Medications prescribed and number of medication changes	X	X	X	X
Medication Adherence	Adherence to Refills and Medication Scale (ARMS)	X	X	X	X
	Pill count	X	X	X	X
	Three-Item Self-rated Adherence Scale	X	X	X	X

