## 5.6 Data Analyses

In this study, we expect to enroll up to 30 physician participants and expect a retention rate of 90-100%. We also expect to enroll about 100 patient participants and expect a retention rate of 80% at the completion of this study.

Data from this study will be analyzed by the study statistician. Survey data will be analyzed using descriptive statistics. Multiple-choice questions will be analyzed using standard quantitative techniques including Chi square and t-test. Open-ended responses will be independently coded using qualitative methods, including any transcripts that result from the recorded survey responses.

Independent sample t-tests will be used to compare outcomes between intervention and control groups at each time point, as well as at similar time points after test results were released to physicians (i.e. baseline for intervention vs. 3 month for control group). Linear mixed models will assess the change in outcomes, as well as whether the change is similar between groups. This will be done by including time, study group, and a time by study group interaction as predictors of each outcome. Time will be considered in two ways, first as the time in study, and secondly as time since test results were released to physicians. In the latter, only data from 3-month to 9-month will be included for the control group, and baseline to 6-month for intervention group, due to timing of test result release. Models will be adjusted for patient demographics.

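### Patients enter by drug for any indication, but section 5.6 compares PHQ-8 and GAD-7 in everyone without using the prescribing reason recorded at baseline

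*Combined protocol and SAP*

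**What the plan says.** **Entry.** Under section 5.4.2 a patient must "Have a new prescription for a certain antidepressant recorded in MiChart" within four weeks before screening, and must be taking the drug. The only related exclusion concerns how long it has been taken. No condition and no PHQ-8 or GAD-7 threshold is named.

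**Expected indications.** The Introduction (2.0) states: "Antidepressants are prescribed for the management of depression, anxiety, and other conditions". A mixed sample is therefore foreseen.

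**Aim 2.** Section 3.0 lists the secondary outcomes as "including change in symptoms and severity and medication adherence from baseline to six-month follow-up". Table 2 schedules PHQ-8 and GAD-7 for every patient at every assessment.

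**Reason for prescribing.** Table 2 has a row "Reason antidepressant was prescribed", marked at baseline and at each follow-up. Under section 5.1, randomisation comes after the baseline assessment is complete, so the baseline answer cannot be affected by arm. Randomisation is stratified by physician only.

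**Analysis.** Section 5.6 plans independent-sample t-tests between arms at each time point, and linear mixed models with time, group and their interaction. On covariates it says only: "Models will be adjusted for patient demographics". Neither the prescribing reason nor a separate baseline-score covariate is named, and no analysis by indication is planned.

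**The concern.** A depression scale and an anxiety scale are applied to patients who may be treated for neither condition, or for only one of them. A patient who scores low on PHQ-8 at baseline because the drug was prescribed for something else has little room to improve on it, whatever the physician does with the test result. The same applies to GAD-7 in a patient treated only for depression.

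There are two consequences. The average difference over all patients would be smaller than the difference in those treated for the scale's condition. In addition, differences in score level and course between indications become unexplained variation in comparisons that ignore indication. With about 80 completers expected, avoidable noise is costly, and a reader of the preliminary effectiveness estimate could not tell a weak effect from a diluted one.

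**Working it through.** The documents give no power calculation, effect size, SD, indication mix or baseline score distribution, so there is no planned figure to reproduce.

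**From the documents.** About 100 patients (5.6), equal allocation (5.1) and 80% retention (5.6): 100 × 0.80 = 80 completers, 40 per arm.

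**Assumed.**
- Two-sided alpha is 0.05.
- q is the share treated for the condition that the scale measures.
- d is the standardised effect in those patients.
- r is the fraction of d that the other patients receive.
- SD is 1 in the treated-for group, and either 1 (equal) or 0.5 (half, as expected near a floor) in the others.

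**Step 1: dilution.** The all-patient effect is d × [q + r(1 − q)]. With r = 0 it is 0.5d at q = 0.5 and 0.8d at q = 0.8.

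**Step 2: restriction against everyone.** With r = 0, and any difference in mean level between indications removed, the z-value in the subset divided by that in everyone is:
- equal SD: 1/√q
- half SD: √{[q + 0.25(1 − q)]/q}

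The value of r above which restriction loses is:
- equal SD: √q/(1 + √q)
- half SD: {√(q[q + 0.25(1 − q)]) − q}/(1 − q)

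| q | z-ratio, equal SD | z-ratio, half SD | break-even r, equal SD | break-even r, half SD |
|---|---|---|---|---|
| 0.3 | 1.83 | 1.26 | 35% | 11% |
| 0.5 | 1.41 | 1.12 | 41% | 12% |
| 0.8 | 1.12 | 1.03 | 47% | 12% |

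At q = 0.5 the entries are 1/√0.5 = 1.41; √(0.625/0.5) = 1.12; 0.707/1.707 = 0.41; and (√0.3125 − 0.5)/0.5 = (0.559 − 0.5)/0.5 = 0.12.

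**Step 3: noise from ignoring indication.** If the two groups differ in mean score by g SDs, an unadjusted comparison carries extra variance q(1 − q)g². With g = 1 and half SD:
- q = 0.5: variance 0.625 + 0.25 = 0.875, so the standard error is √(0.875/0.625) = 1.18 times as large
- q = 0.8: variance 0.85 + 0.16 = 1.01, so the standard error is √(1.01/0.85) = 1.09 times as large

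Seen another way, with 50 per arm and q = 0.5 the standard error of the between-arm difference in indication share is √(2 × 0.5 × 0.5/50) = 0.10. This is the same noise, not a further amount.

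**Step 4: power for d = 0.5, r = 0, 40 completers per arm.** In everyone, power = Φ(qd√20/SD − 1.96). In the subset, power = Φ(d√(20q) − 1.96).

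| q | everyone, equal SD | everyone, half SD, 1-SD gap left in | everyone, half SD, gap removed | subset |
|---|---|---|---|---|
| 0.8 | 0.43 | 0.43 | 0.49 | 0.52 |
| 0.5 | 0.20 | 0.22 | 0.29 | 0.35 |

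If every patient were treated for the scale's condition, power would be 0.61. Under these assumptions, adjustment for reason moves power from 0.22 to 0.29 at q = 0.5 and from 0.43 to 0.49 at q = 0.8, without dropping anyone. Adjustment removes noise; it does not undo the dilution in Step 1.

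**The case against.** The strongest case for the present plan is that its question concerns primary care patients newly prescribed a listed antidepressant, whatever the reason. The all-patient contrast answers that question, randomisation protects it, and the primary outcome in Aim 1 does not depend on indication. The trial is a pilot with no power claim. This stands, and it is why the all-patient comparison should remain the main one.

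It is also fair that a floor is assumed rather than shown. Patients treated for one condition may have symptoms of the other. Conversely, a patient prescribed for depression may already score low at baseline, since up to four weeks of drug before screening is allowed and the Introduction puts onset at two to four weeks. Prescribing reason is therefore an imperfect guide to room for improvement, and baseline score is needed beside it.

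The mixed model on time in study includes baseline as a time point, so its interaction term already absorbs much of any chance difference in level. The noise argument applies mainly to the t-tests, and in the mixed model to different courses over time by indication.

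Three stronger readings are tempting and not supported:
- A reader might infer that any effect on Aim 2 is masked. Under these assumptions the effect shrinks but does not vanish: at d = 0.8 and q = 0.8, all-patient power with equal SD is still about 0.82. The adherence part of Aim 2, with three measures in Table 2, has no such floor.
- A reader might infer bias between arms. Mixed indication under randomisation costs sensitivity only.
- A reader might infer that the indication subsets should become the main analysis. At q = 0.5 that loses sensitivity once other patients receive about 41% of the effect (equal SD) or 12% (half SD), and the documents cannot exclude either.

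**Conclusion.** The point holds as a loss of sensitivity and interpretability in the PHQ-8 and GAD-7 part of Aim 2. Entry is by drug, the protocol foresees several indications, and a pre-randomisation variable that separates them is collected but left out of section 5.6.

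The size cannot be stated from the documents. At an assumed q of 0.5, the z-gain from restriction is about 1.12 to 1.41 if other patients have no benefit, and less or reversed if they have some. Adjusting the all-patient comparison instead cuts the standard error by a factor of about 1.18 under the half-SD, 1-SD-gap assumption. It carries no comparable risk of losing sensitivity, because it keeps every patient. Neither change makes a moderate effect reliably detectable with 40 completers per arm, so the benefit lies in a cleaner and more readable estimate.

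**What to change.** In section 5.6:

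1. Keep the all-patient comparison of PHQ-8 and GAD-7 as the main symptom analysis, and adjust it for the prescribing reason recorded before randomisation and for the baseline score. At single follow-up times, replace the t-test with a regression on arm, baseline score and baseline reason.
2. In the mixed model, add baseline reason and its interaction with time, so that different courses by indication are absorbed. State how baseline score enters: as a covariate with follow-up scores as outcomes, or as one of the repeated outcomes, but not both.
3. Pre-specify as supporting analyses PHQ-8 in patients whose baseline reason includes depression, and GAD-7 in those whose reason includes anxiety. A patient may be in both. Never define these groups from follow-up answers.
4. Define the reason categories before the data are examined by arm, allowing more than one reason per patient. Table 2 names no instrument for this item.
5. Report the indication mix and baseline scores by arm, so that the dilution can be judged.

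Enrolment and data collection do not change. The cost is SAP wording, a few degrees of freedom, and small supporting subsets: at q = 0.5, about 40 × 0.5 = 20 completers per arm.

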## 5.5 Study Evaluations

### **5.5.1 Physician Participants**

Physician participants will be screened for inclusion/exclusion criteria prior to consent and enrollment. After enrollment, all physician participants will complete a baseline survey that assesses demographics and participant characteristics, knowledge of PGx testing, as well as perceptions of the acceptability and utility of PGx testing in primary care. At the conclusion of the study, physician participants will complete a semi-structured interview and survey that will assess

knowledge of PGx testing, whether they recommended PGx testing to other physicians, or ordered PGx testing on patients not included in this study; as well as perceptions of the feasibility, acceptability, effectiveness, and utility of PGx testing in primary care, including barriers to widespread adoption, as well as satisfaction. Surveys/interviews will be audio recorded when permitted by participants. Please see Table 1 for physician participant measures and timing of assessment.

**Table 1: Physician Participant Measures**

Construct	Measure	Assessment Time	
		Baseline	Post-Study
Demographic information and characteristics of physicians	Investigator Developed Semi-Structured Interview and Survey	X	
Knowledge of PGx testing		X	X
Acceptability of PGx testing		X	X
Utility of PGx testing		X	X
Effectiveness of PGx testing		X	X
Feasibility of PGx testing		X	X
Barriers to PGx testing		X	X
Satisfaction with PGx testing		X	X

### **5.5.2 Patient Participants**

Patient participants will be screened for inclusion/exclusion criteria prior to consent and enrollment. After enrollment, all patient participants will complete a baseline, 3-, and 6-month assessment. Control patients will have an additional 9-month assessment of the previously mentioned items. All baseline data will be collected via paper forms and then transferred into REDCap, whereas 3-, 6-, and 9-month assessments will be conducted via phone and entered directly into REDCap by study personnel. The constructs, measures, and data collection times are shown in Table 2. In addition to these measures collected during data collection visits, data will be extracted from MiChart to document treatment, including medication changes, and healthcare utilization for patient participants during the study. We will also extract any available PHQ-9 and GAD-7 data, which is now collected as a part of routine clinical practice. Surveys/interviews will be audio recorded when permitted by participants.

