Patient participants will meet with study staff for consent and baseline data collection at a Michigan Clinical Research Unit (MCRU) in either Domino's Farms or the Cardiovascular Center. Once consent and baseline data collection are complete, participants will have their blood drawn by MCRU laboratory staff. A single 4 mL Lavender top EDTA tube of blood will be drawn. Once the blood draw is complete, study staff will send the sample to Progenity for analysis. After the baseline assessment is complete, patient participants will be randomized equally to either have their test results sent immediately to their participating primary care physicians once available, or to have their test results sent in three months. Randomization will be stratified by physician in ten block units to ensure balance by physician. PharmDs on the research team ([name] and [name]) will be available to consult with physician participants at any time during the study; however, our study PharmDs will meet with each participating physician at least once, when their first patient PGx test results are available to provide general, as well as patient specific education about the PGx test and results. These consultations will help physicians to interpret PGx test results, and may help to guide treatment decisions, if necessary. Study pharmacists or staff will not

provide PGx results to patients; it is up to the patient's physician to provide this information if he/she feels it is appropriate. Likewise, although study pharmacists may make treatment recommendations based on the PGx test results, it is up to the treating physician to decide whether to act on those recommendations. All intervention patient participants will be followed for a total of 6 months, with phone-based follow-up assessments occurring at 3- and 6-months. All control patients will be followed for 9 months, with phone-based follow-up assessments occurring at 3-, 6-, and 9-months. Please see Figure 2 for patient participant study flow.

Figure 1. Physician Participant Study Flow

[figure not shown]
[figure not shown]

Figure 2: Patient Participant Study Flow

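### Patient-reported scales are on paper at baseline and by phone afterwards, so within-arm change and the release-aligned analyses mix survey mode with real change; same-visit comparisons of the arms do not

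*Combined protocol and SAP*

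**What the plan says.** Section 5.5.2 fixes the mode by visit: "All baseline data will be collected via paper forms and then transferred into REDCap, whereas 3-, 6-, and 9-month assessments will be conducted via phone". Follow-up answers are "entered directly into REDCap by study personnel". The column heads of Table 2 agree, from "Baseline (via paper survey" to "9 months (Control Only; via phone", and Section 5.1 confirms it for the control arm: "All control patients will be followed for 9 months, with phone-based follow-up assessments occurring at 3-, 6-, and 9-months". The intervention arm has the same phone visits at 3 and 6 months.

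Specific Aim 2 in Section 3.0 concerns "change in symptoms and severity and medication adherence from baseline to six-month follow-up". Section 5.6 plans:

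- t-tests between arms at each time point;
- t-tests at matched times after results were released ("i.e. baseline for intervention vs. 3 month for control group");
- linear mixed models with time, group and their interaction, run once on time in study and once on time since release. The release-time model uses months 3 to 9 for controls and baseline to month 6 for the intervention arm.

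The models adjust for patient demographics. Mode is not mentioned.

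**The concern.** PHQ-8, GAD-7, SF-12, WPAI, ASEC, ARMS and the three-item adherence scale ask about mood, functioning, side effects and missed doses. Answers on a paper form may differ from answers given to a staff member by phone. No follow-up is on paper and no baseline is by phone, so mode coincides exactly with baseline versus follow-up.

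Within an arm, a mode shift would look like improvement or worsening after testing. In the release-aligned analyses the problem is greater, because there mode differs between the arms as well. Preliminary effectiveness is a stated objective of this pilot, and these contrasts could be read as evidence for it.

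**Working it through.** The documents state no alpha, power, SD or mode effect, so there is no planned figure to reproduce. The check asks which planned contrasts a mode shift reaches, and how much it could matter.

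**Which contrasts are affected.** Let m be a constant phone-minus-paper shift, with no true change and no effect of testing. The expected score is then 0 at baseline and m at months 3, 6 and 9, in both arms.

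| Contrast (Section 5.6) | Expected value |
|---|---|
| Arms at the same study visit | 0 − 0 at baseline, m − m later = 0 |
| Time in study, difference in change, baseline to 6 months | (m − 0) − (m − 0) = 0 |
| Within-arm change, baseline to 6 months | m − 0 = m |
| Release-aligned t-test at release: intervention baseline minus control month 3 | 0 − m = −m |
| Release-aligned difference in change: intervention 0 to 6, control 3 to 9 | (m − 0) − (m − m) = m |
| Release-aligned, 3 and 6 months after release | m − m = 0 |

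The main effect of time carries m in the same way as within-arm change. The zero in the second row holds over the visits both arms share (baseline, 3 and 6 months) or with time as categorical. A straight-line time effect that takes in the control-only month 9 visit need not give both arms the same fitted slope.

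**How large it could be.** Inputs from Section 5.6: about 100 patients and 80% retention, so 100 × 0.8 = 80, or 40 per arm with the equal randomization of Section 5.1 and equal loss. Assumptions not in the documents: m of 0.1, 0.2 or 0.3 SD; within-patient correlation ρ of 0.5 or 0.7; two-sided alpha 0.05.

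Rejection rate = Φ(m/SE − 1.96) + Φ(−m/SE − 1.96), in SD units.

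- Release-aligned t-test: SE = √(2/40) = 0.224.
- SD of change = √(2(1 − ρ)) = 1 at ρ = 0.5 and 0.775 at ρ = 0.7.
- Release-aligned difference in change: SE = SD of change × √(2/40) = 0.224 or 0.173.
- Within-arm change: SE = SD of change / √40 = 0.158 or 0.122.

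| Contrast | m = 0.1 | m = 0.2 | m = 0.3 |
|---|---|---|---|
| Release-aligned t-test | 7% | 15% | 27% |
| Release-aligned difference in change, ρ = 0.5 | 7% | 15% | 27% |
| Release-aligned difference in change, ρ = 0.7 | 9% | 21% | 41% |
| Within-arm change, ρ = 0.5 | 10% | 24% | 48% |
| Within-arm change, ρ = 0.7 | 13% | 37% | 69% |

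A simulation of 20,000 trials per value of m (0, 0.2, 0.3 and 0.5 SD) at ρ = 0.5 agreed. The release-aligned difference in change rejected 14% and 26% of the time at m = 0.2 and 0.3, while the time-in-study difference in change stayed at 5% throughout.

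The 80% retention applies to study completion, so baseline numbers would be larger. With 50 intervention patients at baseline and 40 controls, SE = √(1/50 + 1/40) = 0.212, and the release-aligned t-test rejects 8%, 16% and 29% of the time.

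**The case against.** The strongest reply is that the randomized comparison is intact. In a two-arm trial, the effect of testing on change is estimated by same-visit t-tests and the time-in-study interaction, and a constant shift cancels in both. That stands. A reader might infer that the Aim 2 treatment effect itself is biased; the documents do not support this, because both arms use the same mode at every shared visit.

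Second, the affected contrasts could not isolate testing even with one mode throughout. Patients enter within 4 weeks of a new prescription (Section 5.4.2), and Section 2.0 puts clinical effect at two to four weeks. Intervention baseline against control month 3 therefore also compares patients starting treatment with patients about three months further on. This stands too, so mode adds to that confounding and is not the sole problem.

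Third, no size or direction of a mode effect is documented, and no section says who fills in the paper form. Table 2 suggests self-completion, but staff do meet patients at baseline (Section 5.1). The percentages are therefore illustrations only.

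Fourth, a model with linear time could estimate a step after baseline. It could do so only by assuming the shape of the true trend, and Section 5.6 plans no such term.

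Finally, MiChart extraction includes PHQ-9 and GAD-7 scores that do not depend on the study's survey mode. These are only what happens to be available, do not cover the side-effect and adherence scales, and are not assigned to any check on mode.

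**Conclusion.** The point holds for four planned results on the patient-reported scales: within-arm change from baseline, the main effect of time, the release-aligned t-test at release, and the release-aligned mixed model. In the last two, mode is confounded with arm. For assumed shifts of 0.1 to 0.3 SD, 40 per arm and correlation 0.5, the release-aligned contrasts reject about 7% to 27% of the time instead of 5%, before any contribution from time on treatment. The result rests on a shift that is constant across patients and visits, and on a mode effect whose existence the documents neither show nor exclude.

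Two extensions are not supported. A reader might infer that the primary outcome is affected in the same way. It is the "change in the proportion of patients who are prescribed medications at baseline that are contraindicated according to the PGx test", compared with six months, and rests on prescriptions that MiChart can document, so it is little exposed. A reader might also extend the point to the pill count, but the documents do not say how bottles are handled at either visit, so that would be speculation.

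This is a worthwhile, inexpensive improvement to secondary analyses. It is not a flaw in the randomized comparison.

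**What to change.** For patients still to be enrolled, have the staff who already attend the baseline visit read the PHQ-8, GAD-7, SF-12, WPAI, ASEC, ARMS and three-item adherence scale from the script used for the calls, and enter the answers directly into REDCap. Amend Section 5.5.2 and the Table 2 column head accordingly. The cost is a few extra minutes per patient, partly offset by less paper transcription. Face-to-face administration still differs somewhat from a phone call, so this narrows the mode difference without removing it entirely. A switch during enrolment also leaves two baseline modes, so record the mode for each patient.

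For patients already enrolled on paper, amend Section 5.6 at no data-collection cost:

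- Base Aim 2 inference on same-visit contrasts between arms and on the time-in-study interaction, stated over the shared visits or with time as categorical.
- Drop the t-test of intervention baseline against control month 3.
- Report the release-aligned mixed model and within-arm change from baseline as descriptive, labelled as confounded by both mode and time on treatment.
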